13.3 Suspected Unexpected Serious Adverse Events (SUSAR)	19
13.3.1 Definitions.....	19
13.3.2 Reporting	19
13.4 Other safety data requiring an immediate declaration	19
13.5 Procedures for Handling Special Situations	19
13.5.1 Pregnancy	19
13.5.2 Overdose Management.....	19
13.6 Annual Safety Report	19
14 Data Collection and Management	19
14.1 Monitoring	19
14.1.1 Composition of data monitoring committee.....	19
14.1.2 Interim analysis	19
14.2 Data Collection	19
14.3 Database Management and Quality Control	19
14.4 Statistical Considerations and Data Analysis	19
15 Ethical Considerations.....	20
15.1 Ethical conduct of the study	20
15.1.1 Declaration of Helsinki.....	20
15.1.2 Ethics Committee	20
15.2 Informed Consent	20
15.3 Patient and Study Data Protection	20
15.4 Subject Identification	20
16 Finance and Insurance	20
17 Reporting and Dissemination	21

18	Conflict of Interest Statement.....	21
19	Tables and Figures.....	22
20	References	23

1 Trial Registration/Protocol Summary

Information	
EudraCT number:	
Date of registration:	Application for registration in a clinical trial registry will be done after obtaining approval from the ethics committee
ClinicalTrials.gov:	Please see previous line
Official Title:	Choice of inhalation device in asthma and COPD
Study Phase/Type:	Single center, single visit cross-sectional interventional study without device or investigational product.
Condition:	Asthma and COPD (Chronic Obstructive Pulmonary Disease)
Objectives:	To identify patient/inhalation device mismatch by using objective measurements.
Investigational Product or Medical Device:	NA
Interventions:	The intervention will be a three-step evaluation. Patients will perform a deep voluntary inspiration. This inspiration will be assessed by the investigator. Secondly, the peak inspiratory flow will be measured over 5 different resistances with an In-check Dial device. Subsequently, patients will receive education about good coordination technique, which is necessary for the optimal use of pressured metered dose inhalers (pMDIs). By using a placebo pMDI, the investigator will assess the coordination of the patient. The evaluation of voluntary deep inspiration, PIF's and coordination will be by pass or fail evaluation.
Endpoints:	To assess if the choice of inhaler device category differs when based on objective assessments, as compared to the choice made by the treating physician (during routine clinical practice), which is primarily based on subjective evaluation.
Study population:	Asthma and COPD patients treated with inhaled medications. Subjects will be recruited in the respiratory outpatient clinic in UZ Brussel after a scheduled consultation with their pulmonologist.
Number of patients:	40 COPD patients (GOLD II-IV); 20 patients with severe asthma, 40 patients with asthma aged ≥ 70 y, 40 patients with mild-to moderate asthma aged < 70 y
Overview of study design:	Single center, single visit cross-sectional interventional study without device or investigational product
Statistical Considerations:	Descriptive analysis will be used to describe the prevalence patient/device mismatch. Multiple regression analysis will be performed to identify patient characteristics associated with inability to use the 3 main classes of inhalation devices respectively. Due to the exploratory nature of this study, no formal power calculation can be performed.
Sponsor:	This study is an academic study and has no sponsor.
Inclusion Criteria:	
 - COPD patients (GOLD II-IV) - Patients with severe asthma - Patients with asthma aged ≥ 70y - Patients with mild-to moderate asthma aged < 70y
Exclusion Criteria:	
 - Patients with asthma or COPD not on inhaled therapy for maintenance treatment - Patients younger than 18y - Patients unable to give their informed consent due to mental or physical disability - Patients who don't speak Dutch or French
Target Date of first enrolment:	To be determined. Probably Q4 2021.

Target sample size:	No target sample size calculation could be performed due to exploratory nature of the study (please see above)
---------------------	--

2 Protocol Version History

Version No.	Release Date	Summary of Changes

3 Sponsor/Coordinating Investigator Information

Coordinating Investigator (promotor): [name]. [name]

Sponsor: NA

Principal Investigator [name]

Co-investigators: [name]. [name], [name] (co-promotor), [name], [name]

Additional co-researchers: NA

Statistician

Laboratory (ies): NA

Pharmacy: NA

Study Coordinator: [name]

Study sites and co-investigators: respiratory outpatient clinic UZ Brussel

4 List of Abbreviations

COPD = Chronic Obstructive Pulmonary Disease

FEV1 = Forced Expiratory Volume in one second

FVC = Forced Vital Capacity

ICS = Inhaled corticosteroids

LABA = long acting beta-agonists

LAMA = long acting muscarinic antagonists

GOLD = Global Initiative for Chronic Obstructive Lung Disease

GINA = Global Initiative for Asthma

5 Introduction

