6.1 Study Schematic

Characteristics of the study	
Informed consent procedure:	
 ▪ Available in Dutch and French ▪ Signature and date written by participant
Inclusion criteria:	
 ▪ COPD patients (GOLD II-IV) ▪ Patients with severe asthma ▪ Patients with asthma aged ≥ 70y ▪ Patients with mild-to moderate asthma aged < 70y
Exclusion criteria:	
 ▪ Patients with asthma or COPD not on inhaled therapy for maintenance treatment ▪ Patients younger than 18y ▪ Patients unable to give their informed consent due to mental or physical disability ▪ Patients who don't speak French or Dutch
Collection of data form patient file:	
 ▪ Choice of inhaler by physician (current inhaled maintenance treatment) ▪ GOLD grade and group (COPD patients) ▪ GINA treatment step (asthma patients) ▪ Smoking status ▪ Height ▪ Weight ▪ Age ▪ FEV₁, FVC, PIF if available ▪ Oral corticosteroid maintenance dose
Study assessments:	
 ▪ Voluntary deep inhalation ▪ Peak inspiratory flows (PIF's) ▪ Coordination (through a placebo pMDI)
Reporting to treating physician in case of patient/device mismatch	
 ▪ To avoid prescription of inappropriate inhaler

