6.2 Study Activities

The study will take place in the respiratory outpatient clinic. Patients will be invited to participate in the study after the consultation with the pulmonologist. All pulmonologists have a flowchart regarding the optimal choice of inhaler at their disposition.

Patients will be provided sufficient time to read the informed consent file and to ask questions about the study. After giving their informed consent they will be screened for eligibility by an

investigator. Demographic data and characteristics will be retrieved from the medical record (EMD) of study participants.

The intervention will consist of three different steps.

First, the patient will perform a deep voluntary inspiration. The patient's ability to perform this inspiration will be assessed and scored by the investigator.

Secondly, the peak inspiratory flows (PIF) will be measured with an In-check Dial device over 5 different resistances.

The minimal and optimal peak inspiratory flow rates (PIFRs) differ by device. A minimum flow of 30 L/min is required for most DPI's. The optimal flow varies from 30 L/min to 35, 45, 50, 60 or 65 L/min. (10)

Due to the fact that there is still discussion about the effectiveness of PIF's going from 30 to 60 L/min, an arbitrary cut-off value will be set at 45 L/min. This cut-off value for sufficient PIF will be measured over a moderate resistance to distinguish subtherapeutic from therapeutic levels. (11) If the patient reaches a PIF lower than 45 L/min, the patient will be asked to make a second attempt.

Subsequently, the patient will receive education about the correct coordination, which is necessary in the use of dose inhalers. The patient will be evaluated for sufficient actuation-inhalation coordination, through a placebo pMDI.

The evaluation of the voluntary deep inspiration, PIF and coordination will be by pass or fail evaluation. Subsequently, the fitness of a patient to use any of the three inhaler classes will be determined by using a diagram designed by a Belgian expert group (unpublished to date; courtesy of [name], ULiège).

If a mismatch between prescribed inhaler and suitable inhaler types is found, the treating physician of the patient will be informed. By doing so, we wish to avoid patients receiving prescriptions for inhalers that they cannot use properly.

7 Study Objectives and Endpoints

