7.2 Secondary Objectives

To assess the proportion of patient/device mismatch per patient subgroup.

To assess the fail rates for each objective measurement separately for the entire study population and per patient group.

To correlate the fail rates for each objective measurement separately with patient's characteristics per patient subgroup and overall (age, sex, height, weight, FEV₁, FVC, PIF, GOLD grade and group, smoking status, GINA treatment step, oral corticosteroid dose).

To correlate fail rates for each objective measurement with patient's characteristics.

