9.2 Inclusion Criteria

- COPD patients (GOLD II-IV)
- Patients with severe asthma included in the Belgian Severe Asthma registry aged <70
- Patients with asthma of any severity aged ≥ 70 y
- Patients with mild-to moderate asthma aged < 70y

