14.4 Statistical Considerations and Data Analysis

The promotor and investigators from UZ Brussel's respiratory division will perform the statistical analysis, with the help of VUB statistician [name].

The statistical plan was discussed during a meeting with professor [name] (see below).

Sample size calculation

This is a purely explorative study, since there is no a priori hypothesis to be confirmed. Hence, no formal sample size calculation is possible.

The findings of this study could later on be confirmed and assessed more extensively in larger dedicated studies.

For this study however, it is important that the patient groups be stratified according to their occurrence in society. We believe this will be the case when the in-and exclusion criteria for this study will be applied.

Statistical analysis

Descriptive statistics will be used to describe the prevalence of patient/device mismatch for the entire study population.

The comparison of the prevalence of patient/device mismatch between patient subgroups and the comparison of the fail rates for each objective measurement separately between patient subgroups will be done by means of the Chi-square test and will be visualized in cross-tables.

To study correlations between patient characteristics (independent variables) and pass or fail rates for each of the three test criteria (dependent variables), box-plots will be used for continuous variables (for example weight and length), whereas the Chi-square test will be used for categorical variables (for example diagnosis, age expressed in years, GOLD stage and GOLD group).

15 Ethical Considerations

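### The synopsis promises multiple regression on inability to use each device class, but section 14.4 plans only one-at-a-time box-plots and chi-square on test pass/fail, with age in years treated as a category

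*Protocol*

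**What the plan says.** Three places in the protocol describe the analysis of patient characteristics.

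- Section 1 (protocol summary, Statistical Considerations): "Multiple regression analysis will be performed to identify patient characteristics associated with inability to use the 3 main classes of inhalation devices respectively".
- Section 7.2 (Secondary Objectives): "To correlate the fail rates for each objective measurement separately with patient's characteristics per patient subgroup and overall". A list of characteristics follows, with age first. No method is named beyond correlating.
- Section 14.4 (Statistical analysis): the aim is "To study correlations between patient characteristics (independent variables) and pass or fail rates for each of the three test criteria (dependent variables"). Box-plots serve the continuous characteristics, with weight and length as examples. For the rest, "the Chi-square test will be used for categorical variables (for example diagnosis, age expressed in years, GOLD stage and GOLD group"). Regression is not mentioned.

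Section 6.2 explains how the two kinds of outcome are linked. After the three tests are scored pass or fail, "the fitness of a patient to use any of the three inhaler classes will be determined by using a diagram".

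**The concern.** The synopsis and the statistical section answer the question of which patients have difficulty with inhalers in different ways. They differ in outcome (device class against single test) and in method (joint model against one characteristic at a time). No text says which governs, and the version history table is empty, so neither is marked as superseded. The analysis that is reported could therefore be chosen after the results are known.

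Two rules in section 14.4 are also weak in themselves. Age in years is assigned to a chi-square test with no bands given. The continuous characteristics receive a box-plot only, which is a display and yields neither an estimate nor a test. Age matters here because section 5.4 cites older age among the strongest correlates of incorrect inhaler technique.

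**Working it through.** The protocol gives no power, alpha or effect size for this analysis, so there is no stated figure to reproduce.

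**1. The texts side by side**

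| | Synopsis | Section 7.2 | Section 14.4 |
|---|---|---|---|
| Outcome | Inability to use each of 3 device classes | Fail on each measurement | Pass/fail on each of 3 tests |
| Method | Multiple regression | Not named | Box-plot or chi-square |
| Characteristics | Modelled together | Not stated | One at a time |
| Form of age | Not stated | Not stated | Categorical |

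Three tests are mapped to three classes through a diagram (section 6.2), so the two sets of outcomes are different variables.

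**2. Age in single years**

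Planned N = 40 + 20 + 40 + 40 = 140 (synopsis). The fail rate p is an assumption. An expected fail count of 5 at one age, the usual rule of thumb for chi-square, needs n = 5/p patients of that age. At most 140/n ages (rounded down) can reach it, even if all patients were packed into those ages.

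| Assumed p | n at one age | Most ages that can reach it | Total fails, 140 × p |
|---|---|---|---|
| 10% | 5/0.10 = 50 | 2 | 14 |
| 20% | 5/0.20 = 25 | 5 | 28 |
| 30% | 5/0.30 = 16.7, so 17 | 8 | 42 |

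With assumed uniform ages (asthma below 70: 18–69; asthma 70 or over: 70–89; COPD: 45–84), about 59 single-year ages are occupied. For fail rates of 10% to 50%, 98% to more than 99% of cells then have an expected count below 5.

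**3. Power under each reading of age (illustration only)**

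Everything except the group sizes is assumed:

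- Ages are truncated normal. COPD: mean 64, 68 or 72, SD 8. Severe asthma below 70: mean 50, SD 13. Asthma 70 or over: mean 76, SD 5. Mild-to-moderate asthma below 70: mean 45, SD 14.
- The model is logit(fail) = logit(p) + b × (age − 60)/10, with p = 20% and no effect of diagnosis or severity. A quarter of the asthma patients aged 70 or over are taken as severe.
- There are 2,000 runs per scenario, two-sided 5%. Ranges are over the three COPD mean ages.

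| Analysis of age | b = 0.3 | b = 0.4 | b = 0.5 |
|---|---|---|---|
| Chi-square, single years | 1.2–2.2% | 1.2–3.0% | 2.6–4.4% |
| Chi-square, below 70 vs 70 or over | 40–47% | 63–71% | 82–87% |
| Logistic, continuous age | 58–64% | 83–86% | 95–97% |
| Logistic, plus diagnosis and severity | 57–59% | 81–83% | 95% |
| Logistic, plus 4-level recruitment group | 22–23% | 33–35% | 45–49% |

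Split at 70 against continuous age, at equal COPD mean age: the largest gap is 83.0 − 63.4 = 19.6 points (b = 0.4) and the smallest 96.9 − 87.2 = 9.7 points (b = 0.5). At b = 0.4 the split gives 43–46% against 59–63% when p = 10%, and 73–81% against 92–93% when p = 30%.

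**4. Room for a regression**

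Section 7.2 lists 12 characteristics, counting GOLD grade and group separately. Fails per characteristic: 14/12 = 1.2, 28/12 = 2.3 and 42/12 = 3.5 at 10%, 20% and 30%. A model with all twelve would be overloaded. GOLD grade and group are also recorded only in COPD and the GINA step only in asthma (section 6.1), so they cannot enter one model over all patients.

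**The case against.** The strongest reply is that nothing here is unworkable. The synopsis and section 14.4 do not exclude each other: per-test results can be tabulated and device-class inability modelled in the same report. A reader might infer that the protocol cannot be followed at all, or that section 7.2 also prescribes box-plots and chi-square. Neither is supported. Both analyses can be run, and section 7.2 names no method. What remains is that the synopsis announces an analysis that the statistical section omits, with no statement of which one answers the question. That conflict lies within the current protocol, so it is not a detail left to an analysis plan.

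The age label sits in a list of examples and may be a slip, or may mean the 70-year boundary used for recruitment. This is fair. A reader might infer that the age analysis has almost no power whatever was meant; that holds only for single years. The split at 70 loses far less, though still something.

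The power figures rest on assumed ages, fail rates and slopes. The small cost of adjusting for diagnosis and severity is shown only where these have no effect of their own. The figures illustrate and do not measure harm. Finally, section 14.4 calls the study explorative with no prior hypothesis, so a choice made after the data does less damage than in a confirmatory trial. That limits the weight of the point but does not remove it.

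**Conclusion.** The point holds as an unreconciled difference in outcome and method between the synopsis and section 14.4, together with two poor rules in section 14.4: age in years as a chi-square category, and box-plots alone for continuous characteristics.

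That the single-year reading is unsuitable for 140 patients needs only an assumed fail rate. The loss of about 10 to 20 points for a split at 70 depends on the assumed ages and effects above.

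A reader might also infer that the unadjusted age association is confounded by diagnosis. The protocol gives neither the ages nor the fail rates needed to show that, and the effect may be negligible. Nor is the main result at risk: the primary objective is a descriptive prevalence of mismatch, which does not depend on any of this. The matter should be corrected, as a fault in a secondary exploratory analysis.

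**What to change.** - State the same outcome or outcomes and the same method in the synopsis, section 7.2 and section 14.4. Either add inability to use each device class to sections 7.2 and 14.4 beside pass/fail on each test, or delete it from the synopsis.
- Take age out of the categorical list and analyse it as continuous. If bands are wanted for display, state them.
- Keep the promised regression, as logistic regression for the binary outcome, with a short covariate list fixed before the data are seen. Report odds ratios with 95% confidence intervals, and label the remaining characteristics in section 7.2 as unadjusted description.

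The covariates are for the investigators to choose. The four-level recruitment group is partly defined by age (section 9.2), and adjusting for it would absorb much of the age effect, as the last row of the power table shows. If asthma severity is chosen, one written rule is needed for all asthma patients: the older group is "Patients with asthma of any severity", and section 6.1 collects the treatment step and no severity class.

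The cost is protocol wording and slightly more analysis, with no extra patients or visits. Estimates will be imprecise if fails are few: about 14 events at an assumed 10% fail rate.

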5.1 Overview of Disease Pathogenesis

Pathogenesis of asthma

Asthma is a heterogeneous disease, which is normally characterized by the presence of chronic airway inflammation. Asthma is defined by the history of respiratory symptoms such as shortness of breath, wheeze, cough, chest tightness. These symptoms can fluctuate over time and in intensity in combination with a variable expiratory airflow limitation. (1)

Pathogenesis of COPD

Chronic Obstructive Pulmonary Disease (COPD) is a common, preventable and treatable disease that is characterized by persistent respiratory symptoms and airflow limitation that is due to airway and/or alveolar abnormalities usually caused by significant exposure to noxious particles or gases

an influenced by host factors including abnormal lung development. Significant comorbidities may have an impact on morbidity and mortality.

The most common respiratory symptoms of COPD are cough and/or sputum production, dyspnea. Underreporting of these symptoms by patients can occur.

The most important risk factor for COPD is tobacco smoking. Other environmental exposures such as air pollution and biomass fuel exposure may contribute. (2)

5.2 Epidemiology

Epidemiology of asthma

Currently, 4.3% of the population worldwide has asthma. The prevalence of asthma in the United States is 8.4%. The prevalence of asthma is on the rise. Asthma is more prevalent in black than in white persons. It is remarkable that the prevalence of asthma decreases with each successive higher poverty level group. Asthma has a significant impact on morbidity and mortality. (3)

Epidemiology of COPD

The global prevalence of physiologically defined chronic obstructive pulmonary disease (COPD) in adults aged >40 years is approximately 9-10 per cent. (4)

The worldwide prevalence of chronic obstructive pulmonary disease (COPD) in adults older than 40 years old is approximately 9-10%. COPD is the fifth leading cause of years lost through early mortality or handicap (disability-adjusted life years). Country, sex and age are factors that influence the prevalence of COPD. (2)

5.3 Current Treatments

Treatment of asthma

The current pharmacological treatment of asthma consists of the stepwise approach by GINA. The goal is to optimize the personalized asthma management by assessing, adjusting and reviewing the response to treatment.

The treatment depends on the number of step of GINA. The 5 different GINA steps are characterized by different treatments. Inhaled corticosteroids (ICS), short acting β 2- agonists (SABA) and long acting β 2 agonists (LABA)

There are 3 different types of inhalers: dry powder inhalers (DPI), pressurized metered dose inhaler (pMDI) and soft mist inhalers (SMI).

[figure not shown]
SMI's and pMDI's can be used in combination with an inhalation chamber. (5)

Box 3-5A

Adults & adolescents 12+ years

Personalized asthma management:
Assess, Adjust, Review response

Symptoms
Exacerbations
Side-effects
Lung function
Patient satisfaction

Asthma medication options:

Adjust treatment up and down for individual patient needs

PREFERRED CONTROLLER
to prevent exacerbations and control symptoms

STEP 1
As-needed low dose ICS-formoterol *

STEP 2

Daily low dose inhaled corticosteroid (ICS), or as-needed low dose ICS-formoterol *

STEP 3

Low dose ICS-LABA

STEP 4

Medium dose ICS-LABA

STEP 5

High dose ICS-LABA
Refer for phenotypic assessment ± add-on therapy, e.g. tiotropium, anti-IgE, anti-IL5/5R, anti-IL4R

Other controller options

Low dose ICS taken whenever SABA is taken †

Daily leukotriene receptor antagonist (LTRA), or low dose ICS taken whenever SABA taken †

Medium dose ICS, or low dose ICS+LTRA #

High dose ICS, add-on tiotropium, or add-on LTRA #

Add low dose OCS, but consider side-effects

PREFERRED RELIEVER

Other reliever option

As-needed low dose ICS-formoterol *

As-needed short-acting β_2 -agonist (SABA)

* Data only with budesonide-formoterol (bud-form)

† Separate or combination ICS and SABA inhalers

Low-dose ICS-form is the reliever only for patients prescribed bud-form or BDP-form maintenance and reliever therapy

‡ Consider adding HDM SLIT for sensitized patients with allergic rhinitis and FEV1 >70% predicted

Figure 1: treatment of asthma

Treatment of COPD

The treatment of COPD depends on the group guided by GOLD: group A, B, C or D.

The corner stone of the pharmacological treatment consists of bronchodilatation: LABA (long acting beta-agonists), LAMA (long acting muscarinic antagonists). A triple therapy: ICS, LABA and LAMA, is recommended in COPD GOLD D patients. (6)

